The proposed study tests the novel DilaCheck® device *in vivo*. The target population is women presenting to the hospital for evaluation of labor or admitted to the Labor and Delivery unit for management of the first stage of labor. The Sponsor (Elm Tree Medical Inc.) trains providers working on the Labor and Delivery unit in the use of DilaCheck®. After informed consent, each patient participant is randomized to receive either two cervical dilation examinations with standard methods or two cervical dilation examinations using the device. Two practitioners complete the cervical examinations separately. The primary outcome is inter-examiner agreement between the control and device arms. Secondary outcomes include agreement of subjective measurements with DilaCheck® measurements over time, agreement of providers' device readings with a blinded reviewer's, patient and provider satisfaction, and documentation of adverse events. Planned enrollment is 50 participants over one year. We hypothesize that the device will increase agreement between the two practitioners from about 49% to 90%, as demonstrated in the simulator trial. The long-term objective is to validate DilaCheck® for use in increasing precision in cervical dilation measurements so that this tool may be available to Labor and Delivery providers to enhance quality of care for pregnant mothers. Increased precision in cervical dilation measurements will enable providers

to make better recommendations for admission to the hospital, augmentation or induction of labor, and cesarean section.

The proposed study is a randomized, controlled trial comparing inter-examiner agreement of standard methods for measuring cervical dilation to a novel medical device. The research population is pregnant women in the first stage of labor.

TRIAL PROTOCOL

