Trial Coordination. After training, the Sponsor or the trial coordinator will orient the provider to the study protocol and assign every provider a unique Provider Number. The trial coordinator will arrange with the hospital staff to conduct the trial at scheduled times during the study period. Administration of the trial requires two hospital providers who have been trained to use the device, the trial coordinator,

and a patient.

Patient Enrollment. Hospital providers will screen patients who have been admitted to the Labor and Delivery unit for eligibility. Posters advertising the trial will also be displayed on the Labor and Delivery unit. Once identified, hospital providers will ask eligible patients if they are interested in participating. If a patient indicates interest, the trial coordinator will complete an informed consent. The patient will sign the Patient Informed Consent Form.

Randomization. The trial coordinator will assign the participant a Subject Number from one to 50, in sequential order. (The first patient enrolled is assigned #1, the second enrolled is assigned #2, and so on.) The trial coordinator will then randomize the patient to either the Control Group or the Device Group using a randomization matrix generated by a computer randomization program.

Data Collection. The trial coordinator will inform two trained providers that the patient has agreed to participate in the trial. The trial coordinator will accompany one hospital provider to the patient's hospital room. The second provider will wait outside the room, in a place where s/he cannot hear the interaction in the room. The trial coordinator will re-affirm consent with the patient.

If the patient is randomized to the Control Group: The first provider will introduce him/herself and inform the patient that s/he is going to conduct a cervical examination. The trial coordinator will record the time of the first exam. The provider will complete a cervical examination following the standard techniques s/he uses on a regular basis, using sterile gloves. The provider will dispose of the gloves. The first provider will write his/her measurement of cervical dilation on the first Data Collection Form and fold the sheet of paper. Readings may be integers or fractional answers. The coordinator will take the folded sheet of paper and will not read the value. The first provider will then leave the hospital room. S/he will not speak to the second provider.

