The second provider will enter the hospital room. The second provider will introduce him/herself to the patient and explain that s/he is going to perform a cervical examination. The trial coordinator will record the time of the second exam. The second exam must be completed within 10 minutes of the first exam. The second provider will complete a cervical examination following standard techniques. The provider will write his/her measurement of cervical dilation on a second Data Collection Form, fold the form, and hand it to the trial coordinator. Readings may be integers or fractional answers. The second provider will leave the room.

If the patient is in the Device Group: The first provider will introduce him/herself and inform the patient that s/he is going to conduct a cervical examination and confirm that the patient is ready to proceed. The trial coordinator will record the time of the first exam. The first provider will complete a cervical examination with a DilaCheck® device and sterile gloves using the techniques taught during training.

During or after the examination, before looking at the DilaCheck® device or his/her hand, the provider will verbally report his/her subjective cervical dilation measurement to the trial coordinator. Readings may be integers or fractional answers. The trial coordinator will record this number. The first provider will then look at the DilaCheck® device and read the measurement from the DilaCheck® measuring tape.

The trial coordinator will take a photograph from a secure camera of the DilaCheck® measurement. The trial coordinator may choose to take multiple photographs to ensure a clear image is captured. The coordinator and provider will use a neutral background to ensure no private health information (such as an image of the patient participant or hospital room) is included in the photograph. A white sheet of paper with the subject number will be provided to serve as a blank, secure background for the photograph(s).

The first provider will record two readings of the DilaCheck® measurement. The provider will write his/her measurements on the first Data Collection Form, fold the form, and hand it to the trial coordinator. The first will be his or her reading of the exact DilaCheck® measurement, which may be a fraction (any fraction). The second reading will be his or her reading of the DilaCheck® measurement rounded to the nearest integer; i.e. the second response can only be an integer, not a fraction.

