The first provider will dispose of the gloves and device. The first provider will then leave the hospital room. S/he will not speak to the second provider.

The second provider will enter the hospital room. The second provider will introduce him/herself to the patient and explain that s/he is going to perform a cervical examination. The trial coordinator will record the time of the second exam. The second exam must be completed within 10 minutes of the first exam. The second provider will complete a cervical examination as above using a DilaCheck® device. The second provider and trial coordinator will repeat the same steps as described above for the first provider. The second provider will leave the room.

Patient Survey. The trial coordinator will then ask the patient to answer the questions on the Patient Survey. The survey will elicit relevant biological and demographic variables including age, race, ethnicity, gestational age, weight, and use of epidural anesthesia. It will assess the patient's discomfort with the examinations, confidence in the accuracy of the measurements, and satisfaction with the examinations. Patients will be asked to report any side effects they experienced and to provide any comments they have.

Patient Reimbursement. The trial coordinator will offer the patient a \$25 gift certificate to thank her for participating. The patient will sign a receipt to confirm that she received the gift certificate.

Provider Survey. At the end of the trial, the trial coordinator will ask all participating providers to complete the Provider Survey. The survey will elicit the provider's years of experience, role on Labor and Delivery, opinions about inter-examiner agreement using standard methods and using DilaCheck®, and ease of use and satisfaction with the device. The survey will ask whether providers experienced any adverse events and if their patients experienced any adverse events during the trial. They will have the option to provide comments.

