Photograph Review. The Sponsor will train an independent reviewer to read DilaCheck® measurements. The reviewer will be provided the photographs taken of DilaCheck® measurements. The reviewer will report two measurements for each photograph. The first will be his/her reading of the exact DilaCheck® measurement, which may be a fraction. The second reading will be his/her reading of the DilaCheck® measurement rounded to the nearest integer; i.e. the second response can only be an integer, not a fraction.

Continuous Feedback. After any individual provider completes five examinations with DilaCheck®, the provider will be provided feedback about whether his/her DilaCheck® measurement readings match those of the independent reviewer.

Power Calculation. The planned enrollment in the study is 50 patients. The following assumptions were used for the power calculations. The agreement in the Control Group was projected to be 49%,⁴ and the agreement in the Device Group was projected to be 90%, based on the results of the simulator trial. The standard deviation was projected to be 23, also based on the standard deviation in the prior simulator trial. With a two-tailed test with $\alpha=0.05$, a sample size of five yields 80% power. However, a trial with five participants will not yield the desired robustness in evaluation of a novel medical device. Instead, a sample size of 25 subjects in each group is planned to allow for examinations across a wide range of patients and providers. A sample size of 50 yields a power of 100% to detect a difference between the two methods given the above assumptions.

Statistical Analysis. The statistical analysis will use a two-tailed level of significance of 0.05. Using SPSS, the proportion of examinations in each group for which the two providers' examinations differed will be determined. A Students T test will be performed to determine whether this difference is significant. The number of examinations for which providers' answers differed by one centimeter and by two or more centimeters for each group will be determined. A Students T test will be performed to determine if the frequency of variation of one centimeter significantly differed between groups. A Students T test will be performed to determine if the frequency of variation of two or more centimeters significantly differed between groups. These analyses will be completed for both the fractional and integral (non-fractional) sets of DilaCheck® measurement readings.

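### Primary agreement comparison: in the integer analysis device readings are held to whole centimetres while control readings may be fractional, and neither device reading set is named primary

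*Combined protocol and SAP*

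**What the plan says.** The Protocol Summary states: "The primary outcome is inter-examiner agreement between the control and device arms". It gives no tolerance and no reading set.

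Under Data Collection, each Control Group examiner writes one value: "The provider will write his/her measurement of cervical dilation on a second Data Collection Form" is the instruction for the second examiner, and the first has an equivalent one. On the scale, the plan says "Readings may be integers or fractional answers". No rounded control reading is collected.

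Each Device Group examiner writes two values from the tape. The first is the exact reading, with any fraction allowed. For the other, "the second response can only be an integer, not a fraction". The second examiner does likewise: "The second provider and trial coordinator will repeat the same steps as described above for the first provider".

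Under Statistical Analysis, "the proportion of examinations in each group for which the two providers' examinations differed will be determined", and a Student's t-test compares the arms. Two further t-tests cover differences of one centimetre and of two centimetres or more. Then: "These analyses will be completed for both the fractional and integral (non-fractional) sets of DilaCheck® measurement readings". The section does not say how control readings are handled in the integer run, or which run is primary.

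**The concern.** Agreement by exact match depends on how finely readings are recorded: a coarser grid produces more matches from the same underlying measurements. In the integer analysis the device arm is on a whole-centimetre grid by instruction, while the control arm uses whatever grid each examiner chose. Rounding does not remove every device disagreement (4.0 and 4.5 can become 4 and 5), but it raises exact agreement on average. Part of any device advantage could therefore come from the recording rule.

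In the fractional analysis both arms may use fractions. If the tape is read more finely than control examiners report, exact matches become rarer in the device arm and the comparison leans the other way.

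With neither analysis ranked, conflicting results would leave the trial with no pre-stated answer on its primary outcome. The open allowance for further appropriate analyses, later in the same section, does not settle this.

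A smaller point: differences of 0.5 or 1.5 cm fit neither of the two size categories, although the overall test of whether readings differed still counts them.

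**Working it through.** **The plan's own figures.** Power Calculation gives 49% against 90%, SD 23, two-tailed alpha 0.05, five for 80% power and 100% power at 50. As a comparison of two means, n = 2(1.960 + 0.842)² × 23² / 41² = 4.94, so 5 per group; power at 25 per group is 99.999%. The figures reproduce, reading five as per group, but say nothing about the agreement rule. Applying the planned t-test to 0/1 agreement scores, 49% against 90% at 25 per arm gives 92.3% power by exact binomial enumeration.

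**Assumptions not in the documents.** True dilation is uniform over 1-9 cm. Reader error is normal with the same SD in both arms, so there is no device effect. Agreement means exact equality. Control readings are to 1 cm or 0.5 cm.

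**Agreement on a grid of width g.** The difference between two unrounded readings has SD s = √2 × SD. The chance that both fall in the same cell is

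A(g) = 2Φ(g/s) − 1 − (2s/g)[φ(0) − φ(g/s)].

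For SD 0.5, s = 0.707:
- Whole cm: 0.843 − 1.414 × (0.399 − 0.147) = 0.486.
- Half cm: 0.520 − 2.828 × (0.399 − 0.311) = 0.271.

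SD 0.5 is a natural anchor, because whole-centimetre agreement is then close to the plan's 49% for controls.

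**Mixed control formats.** Let h be the share of half-centimetre readings. If both examiners of a patient use the same format, control agreement is (1 − h)A(1) + hA(0.5). At h = 25% this is 0.75 × 48.6 + 0.25 × 27.1 = 43.2%. If each examiner chooses independently, it was simulated. The pooled t-test was then enumerated exactly at 25 per arm. Device integer agreement is 48.6% throughout.

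| Half-cm control readings | Control agreement, shared / independent | Device falsely better, shared / independent |
|---|---|---|
| 0% | 48.6% | 3.2% |
| 10% | 46.5% / 44.2% | 4.5% / 6.2% |
| 25% | 43.2% / 38.6% | 7.0% / 12.5% |
| 50% | 37.9% / 31.7% | 13.7% / 25.5% |
| 100% | 27.1% | 37.4% |

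A two-sided 0.05 test should give about 2.5% in this direction. Across SD 0.2-0.8 cm the ranges at 10%, 25% and 50% are 4-5%, 5-8% and 9-16% with shared formats, and 5-8%, 8-19% and 16-39% with independent ones. At 100% the range is 26-45%.

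**Fractional set (stress cases, because the tape graduation is not given).** Take the plan's 49% and 90% as whole-centimetre agreement. That implies SD 0.495 for controls and 0.089 for the device. Exact device agreement then falls to 80%, 61% or 30% if the tape is read to 0.5, 0.25 or 0.1 cm. With whole-centimetre controls, the chance of a device win is about 92% in the integer set, but 67%, 16% or 0.1% in the fractional set. The two sets give different verdicts in 30%, 77% or 98% of simulated trials. If all controls are in half centimetres, the fractional-set win rates are 98%, 72% and 4%, and verdicts differ in 2%, 28% or 96% of trials.

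**Size categories.** Over SD 0.2-0.8 with shared formats, 16-38%, 31-63% and 56-96% of control disagreements fall in neither category at 25%, 50% and 100% half-centimetre use. For integer readings the figure is 0%.

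**Candidate remedies, equal reader error.**
- Rounding the unrounded readings of both arms by one programmed rule (halves up) gives 3-6% false device wins for every mix and tape grid tested.
- A tolerance on unrounded readings does not equalise the arms. With whole-centimetre controls, within 0.5 cm gives 6-70% false device wins, and within 1 cm gives up to 24% false device losses.
- A t-test on absolute differences gives 1-6% false wins and 1-5% false losses.

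**The case against.** The strongest reply has four parts.

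- **A rule exists.** Counting pairs that differed can be read plainly as exact equality. That is fair, and the calculations use it. But one literal rule on two recording grids is not a common rule for the two arms.
- **The integer-set bias is conditional.** The protocol permits fractional control readings but does not say how common they will be. With none there is no bias, and at 10% with shared formats it is negligible (4-5% against about 3%). The largest figures also come from reader SDs of 0.2-0.3 cm, where whole-centimetre agreement would be 77% or 66% rather than 49%. This stands, so the SD 0.5 row values should carry the argument. The fractional-set figures show what is possible and are not forecasts.
- **Both analyses are declared in advance**, so a reader would see any conflict. True, but declaring two analyses without ranking them does not say which one answers the primary question.
- **Nothing says the rule would be chosen after seeing data.** Also true. The Sponsor Review paragraph concerns monitoring, and giving hospital staff access to the analysis is a safeguard. Still, the Sponsor sees all collected data monthly and is the party that shares the analysis, so a rule fixed late could not be shown to be independent of the results.

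Programmed rounding is also imperfect, because a reading already rounded to 0.5 cm is rounded again. With independent 50/50 formats, false device wins are 3.8% at SD 0.5 and 5.6% at SD 0.2. They reach 11% at SD 0.1, which is outside the tested range but near the device SD implied above.

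**Conclusion.** The concern holds. The plan records the arms on different scales, scores exact differences, rounds only the device readings in the integer analysis, and ranks neither analysis. The direction of the integer-set bias needs only some fractional control readings.

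Its size depends on reader error and on how often control examiners use half centimetres. At SD 0.5 cm the rule alone lowers control agreement by about 5-10 points when a quarter of control readings are half-centimetre (48.6 − 43.2 and 48.6 − 38.6), and by about 11-17 points when half are (48.6 − 37.9 and 48.6 − 31.7). Which way the fractional set leans, and how often the two sets conflict, depends on how finely the tape is read.

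This should be fixed because it touches the primary outcome. It does not spoil the data: unrounded readings are collected in both arms, so one rule can be applied at analysis.

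**What to change.** In Statistical Analysis, before results are seen:

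1. Define agreement by one rule applied identically to both arms, and name it the single primary analysis. One example is to round the unrounded readings of both arms to whole centimetres by program, with the treatment of halves stated. The choice is the sponsor's, but the rule should put both arms on the same grid. If a tolerance is preferred, apply it after that step.
2. Label the other reading set secondary, and add the absolute between-examiner difference in centimetres, analysed in both arms, as a secondary measure.
3. Replace the two size categories with exhaustive ones in both arms: 0, above 0 to below 1, 1 to below 2, and 2 cm or more.
4. Optionally, if recruitment is not complete, add a line to the control form for the examiner's own whole-centimetre reading.

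The cost is a few sentences of analysis text and possibly a less favourable device result. No extra patients, examinations or data are needed; the optional line is one more entry per control examination.

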For participants in the DilaCheck® arm, the subjective and DilaCheck®

DilaCheck® Trial

measurements will be plotted along an X-Y axis and the Pearson correlation coefficient between the two data sets will be calculated. This analysis will be completed for both the fractional and integral (non-fractional) sets of DilaCheck® measurement readings.

The photographs of the DilaCheck® measurements will be read by an independent, blinded reviewer to report the DilaCheck® measurements. The provider's and reviewer's DilaCheck® measurements will be plotted along an X-Y axis and the Pearson correlation coefficient between the two data sets will be calculated. This analysis will be completed for the fractional and integral (non-fractional) sets of DilaCheck® measurement readings.

The correlation between the providers' subjective and DilaCheck® measurements will be analyzed over time. To do so, for providers who complete at least 10 exams, the correlation of the two measurements in the provider's first half of examinations will be compared to the providers' second half of measurements. A T-test will be completed to determine whether the two correlations differ significantly. The analysis will be repeated for both the fractional and integral (non-fractional) sets of DilaCheck® measurement readings and using the data sets of readings from the independent reviewer.

The average pain score in each group will be calculated, and a Students T test will be performed to determine whether pain scores differed significantly between groups. Using logistic regression whether provider number, patient age, gestational age, weight, or epidural status significantly impacted likelihood of agreement or pain score within each group will be determined. The average provider confidence in accuracy will be calculated, and a Students T test will compare if patients' confidence differs significantly between groups. Logistic regression will be used to determine if provider experience or training significantly predicted likelihood of agreement.

Any additional statistical analysis appropriate for the data collected will be performed. For the qualitative data, including descriptions of adverse events and feedback, each of the responses will be reviewed individually. Any serious adverse events will be reported. Any informative feedback or themes in the feedback will also be collated.

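### Two secondary outcomes defined as agreement are analysed only with an X-Y plot and Pearson correlation, which ignores a constant offset; comparing correlations over time has the same blind spot

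*Combined protocol and SAP*

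**What the plan says.** The Protocol Summary lists among the secondary outcomes "agreement of subjective measurements with DilaCheck® measurements over time, agreement of providers' device readings with a blinded reviewer's". Both are agreement outcomes.

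The Statistical Analysis section gives each pairing an X-Y plot and a Pearson coefficient, on the fractional and the integer device readings. For provider against photograph reviewer it says: "The provider's and reviewer's DilaCheck® measurements will be plotted along an X-Y axis and the Pearson correlation coefficient". For change over time it says: "The correlation between the providers' subjective and DilaCheck® measurements will be analyzed over time". The method, restricted to a subset ("for providers who complete at least 10 exams"), is that "the correlation of the two measurements in the provider's first half of examinations will be compared to the providers' second half of measurements", followed by: "A T-test will be completed to determine whether the two correlations differ significantly".

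Four other places come close to an agreement measure, but none supplies one for these pairings:

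- The difference analysis ("the proportion of examinations in each group for which the two providers' examinations differed will be determined") and the counts of one and of two or more centimetres compare the two providers with each other.
- The logistic regressions on likelihood of agreement, read in context, also concern the two providers. One set is run within each group, and the control group has no device reading or photograph.
- Under Continuous Feedback, providers learn whether their readings match the photograph reviewer's. This is a procedure, not an analysis.
- The closing provision ("Any additional statistical analysis appropriate for the data collected will be performed") names no measure.

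**The concern.** Agreement asks whether two readings are the same, or how many centimetres apart they are. Pearson r asks whether the points lie close to some rising straight line. A provider who always estimates 1 cm above the device has perfect correlation and no matching readings. The coefficient also rises when a wider range of dilations is enrolled, even if reading error is unchanged.

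A high r could therefore be reported as good agreement while a consistent gap goes unestimated. The comparison over time inherits the problem: if practice with the device removes a provider's consistent bias, r need not move, and the result could be reported as no change. The trial aims to validate a measuring device, and the document counts errors in whole centimetres, so a consistent gap is something these outcomes should be able to show.

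**Working it through.** The plan states no figure for these analyses, so there is none to reproduce.

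**Inputs from the document.** 25 patients per group, two exams per patient, two-tailed alpha 0.05, at least 10 exams for the over-time analysis.

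**Assumptions, because the document gives no values.** Uniform dilation over 1-9.5, 1-6 or 2-5 cm; random error SD s = 0.5 cm; offset 1 cm; difference SD 0.7 cm and provider ICC 0.1-0.3 for precision.

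**1. Pearson r against agreement.** For any constant a and any b > 0, corr(x, a + by) = corr(x, y). With one reading equal to the other plus independent error, r = sqrt(V/(V + s²)), where V = range²/12 and s² = 0.25.

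| Dilation range | V | r, no offset | r, 1 cm offset | Integer match, no offset | Integer match, 1 cm offset |
|---|---|---|---|---|---|
| 1-9.5 cm | 8.5²/12 = 6.02 | 0.98 | 0.98 | 61% | 18% |
| 1-6 cm | 5²/12 = 2.08 | 0.94 | 0.94 | 61% | 19% |
| 2-5 cm | 3²/12 = 0.75 | 0.87 | 0.87 | 61% | 19% |

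Match percentages are simulated, with both readings rounded to the nearest centimetre. Across each row r does not move while matching falls by about two thirds. Down each column r moves from 0.98 to 0.87 although reading error is identical. A difference-based summary separates the cases: limits of agreement are 0 ± 1.96 × 0.5, or -0.98 to 0.98 cm, without the offset, and 1 ± 0.98, or 0.02 to 1.98 cm, with it.

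**2. How many providers can enter the over-time analysis.** Only device exams give both a subjective and a device reading. If the threshold means device exams, 25 × 2 = 50 exams allow at most 50/10 = 5 providers, with five pairs per half at that maximum.

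**3. What the over-time test can see.** Suppose a common 1 cm offset is present in the first half and gone in the second. Each provider's true correlation is the same in both halves, so a test of correlations rejects only at its false-positive rate. In simulation (40,000 runs, five providers × five pairs per half) it flags a change in 2-5% of trials, whether by provider or pooled. A paired t-test on provider mean differences gives:

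| Providers × pairs per half | Signed / absolute, same offset in all | Signed / absolute, offset varying between providers with SD 0.5 cm |
|---|---|---|
| 5 × 5 | over 99% / 97% | 80% / 59% |
| 3 × 8 | 91% / 75% | 41% / 23% |
| 2 × 12 | 41% / 31-32% | 16% / 11% |

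Two other patterns, with five providers:

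- Offsets of +1 cm in three providers and -1 cm in two, then removed: the by-provider correlation test flags 2-5%, the pooled one 55-80%, signed differences 0% and absolute differences 97%.
- An offset fading from 1 to 0 cm within the first half: the correlation tests flag 4-9%, signed differences 75% and absolute differences 46%.

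**4. Precision of the proposed mean difference.** Ignoring clustering, 1.96 × 0.7/√50 = ±0.19 cm. With m exams per provider, multiply the standard error by sqrt(1 + (m - 1) × ICC).

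- Five providers × 10 exams: the factor is 1.38 (ICC 0.1) to 1.92 (ICC 0.3). With the t quantile on 4 df (2.776), the half-width is ±0.38 to ±0.53 cm.
- Two providers × 25 exams: the factor is 1.84 to 2.86. With the t quantile on 1 df (12.7), it is about ±2.3 to ±3.6 cm, which is uninformative.

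**The case against.** The strongest reply has four parts.

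**Size of the offset.** Provider and photograph reviewer read the same tape, and the document reports 96% device accuracy in the simulator with no reading wrong by more than 1 cm. A uniform 1 cm offset in that pairing is hard to credit. This stands. A reader might infer from the table that provider and reviewer readings are likely to be 1 cm apart; the document does not support that. A systematic gap is more plausible for subjective against device readings. The choice of statistic is still wrong for both pairings, because r would not show a gap of any size.

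**The plot.** An X-Y plot shows the raw pairs, so a uniform shift could be seen by eye. True, but no line of identity, estimate or interval is planned.

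**The over-time test is not always blind.** The plan does not say whether halves are pooled across providers. If they are, offsets in opposite directions are often detected. This stands: the blind spot is certain only for an offset that is constant within each provider's first half and either common to all providers or analysed provider by provider.

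**Few providers.** Much of the weakness over time comes from their number, which a change of statistic does not cure. This also stands. A reader might take 99% and 97% as the power of the replacement. Those figures need the arithmetic maximum of five qualifying providers and an identical offset in each. The Benchmarks section asks only that at least two providers be trained.

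**Conclusion.** The mismatch is real and follows from the text: two outcomes are worded as agreement, and the only named analyses are an X-Y plot, Pearson r and a test of two correlations. The invariance of r to offset and positive scale is exact (rounding to integers can disturb it slightly). The sizes, such as r of 0.98 alongside either 61% or 18% matching, rest on the assumed dilation range, error SD and offset.

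The over-time point is secondary. Comparing correlations cannot detect a common offset that disappears between halves. Comparing differences can, but with two or three qualifying providers the result is weak and should be treated as exploratory.

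A reader might infer that the trial's main conclusion is at risk. It is not: the primary outcome compares the two providers' readings directly and does not use Pearson r. The change should be made, but it concerns secondary outcomes only.

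**What to change.** In the Statistical Analysis section:

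- For both pairings, and for the fractional and the integer reading sets, report the mean difference with 95% limits of agreement and the percentages identical and within 1 cm. State how fractional subjective readings are rounded for the integer comparison.
- Add the line of identity to the X-Y plots and keep Pearson r as descriptive only.
- Replace the T-test of correlations with signed and absolute subjective-device differences, early against late, shown by provider and labelled exploratory. Both are needed, because signed differences cancel when providers err in opposite directions.
- Use intervals that allow for two exams per patient and repeated exams per provider. Resampling patients alone does not cover provider clustering. If only two or so providers contribute, describe each provider's mean difference rather than fit a model.

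The cost is a change of wording and a little more analysis. All paired readings are already collected, and no procedure or sample size changes. Precision will be limited, and the number of contributing providers should be reported beside every interval.
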